7.2.2 Per-Treatment Evaluable Population

The per-treatment evaluable (PTE) population will consist of all subjects and sinuses that were successfully treated with the UP Drug-Coated Device on the treatment side and with the UP Control Device on the control side, have had no major procedural protocol deviations (i.e., if a study subject was treated before signing an ICF, or sinuses received a treatment not consistent with the randomization assignment), and have follow-up data available. Reasons for exclusion from PTE will be provided in data listings.

8 GENERAL DATA DERIVATIONS

8.1 Study Day Calculation

Study day 0 is the day of the baseline balloon dilation procedure. Study day is calculated relative to baseline procedure (Study day 0) and will appear in the listings where applicable.

If the date of event is on or after the date of the baseline procedure, study day will be calculated as:

$$\text{Study day} = \text{date of event} - \text{date of procedure}$$

8.2 Baseline

The baseline is defined as the last observation recorded prior to the initiation of the baseline procedure.

8.3 Study Visits

Subjects in the PK cohort will return for 6 follow-up visits at Day 1 (24-hour following the baseline procedure), 3, 7, 14, 21, and 30. Subjects in the randomized cohort will return for 5 follow-up visits at Days 7, 14, 21, 30 and 60 (end of study).

Subjects in both PK and randomized cohorts may come in for additional unscheduled office visits, if clinically necessary. Data from the unscheduled visits in the randomized cohort will be handled as described in [Section 9.2](#).

8.4 Role of the Independent Reviewer

Video-endoscopies of the FSO at Day 14 and Day 30 from all subjects in the randomized cohort will be provided to an independent sinus surgeon reviewer for grading and determination of the primary and secondary efficacy endpoints. The reviewer will be independent from the study (i.e., not enrolling study subjects for the study) and masked to treatment assignment (i.e., not know which sides received the UP Drug-Coated Device and the UP Control Device). To reference the subjects' pre-dilation anatomy as needed, the independent reviewer will have access to the pre-procedure videos.

Video-endoscopies obtained pre-procedure, at Day 14 and at Day 30 will be labeled with subject ID and will be checked to ensure no subject-identifying information (e.g., images of subjects' face) is included before being provided to the independent reviewer.

9 STATISTICAL METHODS

9.1 Randomization

Eligible subjects in the randomized cohort will have their sinus sides randomly assigned to receive the UP Drug-Coated Device in one FSO (treatment side) while the contralateral FSO (control side)

will receive the UP Control Device. The ratio of left to right FSO assignments will be 1:1. The randomization scheme will be generated by a biostatistician consultant and the randomization envelopes will be assembled by an in-house clinical research associate. The randomization scheme will be stratified by each clinical center. To maintain blinding of study personnel to the treatment assignment, the treatment and control devices will be designated with a letter such as Device C and Device D. The information inside the randomization envelope will indicate which FSO side receives which device letter with no information regarding the treatment or control device (e.g., Device C – LEFT, Device D – RIGHT).

9.2 General Statistical Considerations

The primary endpoint, all secondary efficacy endpoints, and safety evaluations will be analyzed for each study cohort separately. The analysis of each cohort will stand on its own; achieving the primary objective in one cohort is considered sufficient for outcomes in that cohort, regardless of the results in the other cohort.

All analyses described in this plan for the randomized cohort are considered *a priori* analyses in that they have been defined prior to locking the database and reviewing unblinded results. All other analyses, if any, designed subsequent to locking the database will be considered *post-hoc* analyses and will be considered exploratory. Any *post hoc* analyses will be clearly identified in the clinical study report.

9.3 General Statistical Procedures

Statistical summaries, confidence intervals (CI), and p-values will be generated using SAS® software. Descriptive statistics will consist of means, standard deviations (SD), median, and ranges for continuous data; and counts and percentages for categorical data. Data from the protocol-specified visits (i.e., as reported in the case report form, CRF) will be used in the summary tables and data listings.

9.3.1 PK Cohort

Data from the pharmacokinetic (PK) assessments of plasma MF, plasma cortisol, and 24-hour urinary cortisol concentrations, endoscopic and SNOT-22 scores will be expressed using descriptive statistics, including but not limited to, means, SD, medians, ranges and, where appropriate, coefficient of variation (%). The PK and cortisol parameters, C_{\max} , C_{24} , T_{\max} , and AUC_{0-24} will be calculated by non-compartmental methods according to the definitions below. Nominal sample times will be used in the calculation of all parameters.

C_{\max}	Maximal concentration after the baseline procedure.
T_{\max}	Time at which maximal concentration after the baseline procedure
C_{24}	PK and cortisol concentration 24 hours after the baseline procedure.
AUC_{0-24}	Area under the concentration-time curve from time 0 to 24 hours. The linear/log trapezoidal rule will be used.

Measurement of urinary cortisol excretion for 24 hours prior to the baseline procedure and for 24 hours after the baseline procedure will be analyzed using a validated bioanalytical method with a LLOQ of 1.00 ng/mL.

A_e	The amount of cortisol excreted in urine, will be calculated by multiplying the volume of urine collected over the 24-hour period by the concentration of cortisol measured in the urine sample.
ΔA_e	The change in cortisol urine exposure following administration- calculated as A_e for the 24 hours after baseline procedure minus A_e for the 24 hours prior to the baseline procedure.

The 24-hour urinary cortisol data will be tabulated for each subject for whom amounts are quantifiable.

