16.3 Analysis of Primary Endpoints

PK cohort

The primary efficacy endpoint is the number of successful balloon dilations, which will be reported with descriptive statistics. The left and right sides of each subject will be considered independent, and each subject is expected to contribute up to 2 observations. The study will be considered successful if $\geq 80\%$ of attempted FSO are dilated successfully with no USADE related to the investigation device. A successful FSO dilation is one in which the physician has inserted the UP Drug-Coated Device into the targeted FSO, followed by 2 consecutive, complete inflations of the balloon.

Continuous data from the plasma MF, plasma cortisol and 24-hour urinary cortisol concentrations will be expressed using descriptive statistics, including but not limited to, means, standard deviations, medians, ranges and, where appropriate, coefficient of variation (%).

Randomized cohort

The primary efficacy endpoint is the difference in the patency grade between treatment sides at Day 30 as determined by an independent, blinded sinus surgeon based on the centralized video-endoscopy review.

The primary efficacy endpoint will be analyzed using the paired t-test.

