6.3 Safety Evaluation

6.3.1 PK Cohort

Systemic Safety: In the PK cohort, systemic safety will be evaluated via measurements of plasma mometasone furoate (MF) and cortisol concentrations and 24-hour urinary cortisol excretion.

- Morning plasma MF and cortisol concentrations before the baseline procedure and at 0.5, 1, 2, 4, and 24 hours after dilation, and again in the mornings of Day 3, 7, 14 and 30 will be tabulated.
 - A validated bioanalytical method for human plasma MF with a lower limit of quantification (LLOQ) of 0.25 pg/mL.

- A validated bioanalytical method for human plasma cortisol with a LLOQ of 1.00 ng/mL
- Measurement of urinary cortisol excretion for 24 hours prior to the baseline procedure and for 24 hours after the baseline procedure
 - A validated bioanalytical method for human urinary cortisol with a LLOQ of 1.00 ng/mL

AEs reported by subjects between enrollment (i.e., consent date) through Day 30 follow-up visit will be tabulated. Each AE will be evaluated by clinical investigators in terms of seriousness, severity (i.e., mild, moderate, severe) and strength of relationship (i.e., not related, unlikely related, probably related, definitely related) to study drug, study device, accessory devices, and baseline procedure.

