10.3 Primary Endpoints

10.3.1 PK Cohort – Primary Endpoint

The primary endpoint is the number of successful sinus dilations of all attempted FSO using the UP Drug-Coated Device. The left and right sides of each subject will be considered independent, and each subject is expected to contribute up to 2 observations. The study will be considered successful if $\geq 80\%$ of attempted FSO are dilated successfully with no USADE related to the UP Drug-Coated Device. A successful FSO dilation is defined as insertion of the UP Drug-Coated Device into the targeted FSO followed by 2 consecutive complete inflations.

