10.7 Safety Measures

In the PK cohort, continuous data from the plasma MF, plasma cortisol and 24-hour urinary cortisol concentrations will be expressed using descriptive statistics, including but not limited to, mean, SD, medians, ranges and, where appropriate, coefficient of variation as described in [Section 9.3.1](#).

Adverse events will be coded using the Medical Dictionary for Regulatory Activities (MedDRA). Where possible, and if applicable, AE will be localized to a sinus type and side. If a subject reports the same AE more than once or experiences the same AE on multiple occasions, the maximum severity grade and relationship to the study drug, study device, accessory devices, and/or dilation procedure will be presented.

The incidence and percentages of AE and serious adverse events (SAE) through Day 30 in the PK cohort and through Day 60 in the randomized cohort, including adverse device effects and USADE, will be presented by MedDRA system organ class (SOC) and preferred term (PT). Complete subject listings of all AE will be provided. For each AE, the following will be specified:

- Start and stop dates, and event onset (study day)
- The affected side (right or left) if available
- Seriousness
- Severity
- Strength of relationship
- Action taken
- Outcome

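### SAP 9.3.1 can leave a subject with unquantifiable post-procedure urinary cortisol out of the urine table, and no rule covers results below the LLOQ

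*SAP*

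**What the plan says.** SAP 6.3.1 names 24-hour urinary cortisol excretion as a systemic-safety measure, alongside plasma MF and plasma cortisol, and specifies "A validated bioanalytical method for human urinary cortisol with a LLOQ of 1.00 ng/mL".

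SAP 9.3.1 opens by committing to descriptive statistics for plasma MF, plasma cortisol and 24-hour urinary cortisol, with no condition on quantifiability. It repeats the urine LLOQ and then defines two quantities. Ae is obtained by "multiplying the volume of urine collected over the 24-hour period by the concentration of cortisol measured in the urine sample". ΔAe is described as "The change in cortisol urine exposure following administration" and is the post-procedure Ae minus the pre-procedure Ae. The section closes with: "The 24-hour urinary cortisol data will be tabulated for each subject for whom amounts are quantifiable".

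SAP 10.7 again promises descriptive statistics for the same three measures ("ranges and, where appropriate, coefficient of variation as described in" Section 9.3.1). Protocol 16.3 says the same, also without a limit: "Continuous data from the plasma MF, plasma cortisol and 24-hour urinary cortisol concentrations will be expressed using descriptive statistics".

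Neither document gives a value to use for a result below the LLOQ or asks for a count of such results. The SAP's statement that all available data will be presented is in Section 9.3.2 and covers the randomized cohort only.

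**The concern.** Steroid exposure that suppresses the adrenal axis lowers cortisol, and Protocol 15.1 lists alteration of that axis as a risk of steroids. If inclusion in the urine table depends on the cortisol amount being quantifiable, it depends on the safety outcome itself. The subject most likely to be left out after the procedure is the one with the largest fall.

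In a cohort of five, one omission is 20% of the data. What is at stake is a descriptive safety summary that could show little or no change when one subject had near-complete loss of urinary cortisol.

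The direction is not the same for both collections. Leaving out a subject because the pre-procedure result is unquantifiable would hide an apparent rise, not a fall.

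**Working it through.** The plan states no figure that depends on this rule, and the PK cohort size was not chosen on statistical grounds, so there is nothing to reproduce. The check has two parts.

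**1. The text, in order**
- Ae needs a measured concentration. A sample below the LLOQ has none, so Ae cannot be computed as defined.
- ΔAe needs Ae from both collections, so it cannot be computed either. This is an inference from the definitions; the SAP does not state it as a separate rule.
- The closing sentence of 9.3.1 then restricts tabulation to quantifiable amounts.
- The opening sentence of 9.3.1, SAP 10.7 and Protocol 16.3 carry no restriction. Section 10.7 refers back to 9.3.1 and neither repeats nor corrects the limit. A mean over all five subjects would in any case need a value for a result below the LLOQ, and none is given.

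**2. Size**

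From the documents: LLOQ 1.00 ng/mL = 1.00 mcg/L; n = 5. Assumed: 24-hour volume V of 1 to 3 L; baseline Ae of 10 to 40 mcg/24 h.

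Fall needed before a subject becomes unquantifiable = 1 − (1.00 × V) / baseline Ae:

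| Baseline Ae (mcg/24 h) | 1 L | 1.5 L | 2 L | 3 L |
|---|---|---|---|---|
| 10 | 90% | 85% | 80% | 70% |
| 20 | 95% | 92.5% | 90% | 85% |
| 40 | 97.5% | 96.25% | 95% | 92.5% |

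Illustration: all five subjects at 20 mcg/24 h before the procedure, V = 1.5 L, four unchanged, one below the LLOQ afterwards.
- Bounds for that subject's post-procedure Ae: 0 and 1.00 × 1.5 = 1.5 mcg.
- ΔAe for that subject: 0 − 20 = −20.0, or 1.5 − 20 = −18.5 mcg.
- Subject omitted: n = 4, mean ΔAe = 0.0, lowest 0.
- Subject kept: n = 5, mean ΔAe = −20.0/5 = −4.0, or −18.5/5 = −3.7 mcg (−20% or −18.5% of baseline); SD 8.94 or 8.27; median 0.
- With the midpoint LLOQ/2 (0.75 mcg): ΔAe = −19.25, mean −3.85 mcg (−19.25%).

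Across the assumed grid, with four subjects unchanged, the mean is −20% of baseline at the zero bound. At the LLOQ bound it is −(Ae − V)/(5 × Ae), which runs from −(10 − 3)/50 = −14% to −(40 − 1)/200 = −19.5%. With the subject omitted it is 0 throughout. The choice of substitution therefore matters much less than the omission.

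Reverse case, pre-procedure result below the LLOQ and 20 mcg afterwards: omission hides a mean rise of +3.7 to +4.0 mcg.

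**The case against.** The strongest reply is that the sentence is ambiguous and does not mention the LLOQ. Amount is the SAP's own term for Ae, and an amount can also be unquantifiable because the 24-hour collection was incomplete or its volume unknown. On that reading the sentence guards against partial collections, which give a falsely low Ae. It also does not say that both collections must be quantifiable, so a subject with a valid pre-procedure amount might still appear. This stands as a limit. The assay reading remains the more natural one, because the LLOQ is given in the same section, and the fix should keep the protection against partial collections.

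Three further points stand:
- Plasma cortisol is tabulated as well ("Morning plasma MF and cortisol concentrations before the baseline procedure and at 0.5, 1, 2, 4, and 24 hours after dilation", then Days 3, 7, 14 and 30), so urine is not the only route to a suppression signal. No rule for results below the LLOQ is given for plasma either.
- The table and listing mock-ups (SAP Appendices B and C) are not visible. A count or footnote for results below the LLOQ may be there.
- The contrast in means follows from the assumed scenario, and the documents give no basis for its probability.

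A reader might infer that SAP 10.7 adopts the exclusion through its cross-reference. The text does not support that: what 10.7 repeats is the unrestricted promise of descriptive statistics. A reader might also infer that a table with n = 4 would give no reason for the missing subject. That cannot be known without the mock-ups.

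**Conclusion.** The point holds as a defect in how the SAP handles urinary cortisol results below the LLOQ. On its natural reading, the closing sentence of 9.3.1 selects on a named safety outcome, and it sits uneasily with the unrestricted commitments in the same section, in SAP 10.7 and in Protocol 16.3. For an unquantifiable post-procedure collection, the lean is toward no suppression.

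Under the assumed volumes and baselines, it takes a fall of more than 70% to 97.5% to trigger the omission. One such subject with four unchanged would move mean ΔAe by about 14% to 20% of baseline. Only the LLOQ and the cohort size come from the documents.

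It would be too strong to infer that the PK cohort's success is in doubt. That rule requires at least 80% of attempted ostia to be "dilated successfully with no USADE related to the UP Drug-Coated Device" and does not use the cortisol summaries. The randomized cohort is not touched. The change should be made, but it concerns a descriptive summary only.

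**What to change.** Replace the closing sentence of SAP 9.3.1 with:

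> Urinary cortisol will be tabulated for all subjects with a complete 24-hour collection, for each collection. Incomplete collections will be flagged and listed with the reason and left out of Ae and ΔAe. Results below LLOQ will be shown as <LLOQ with their count before and after the procedure, and Ae and ΔAe will be summarised with those values set to 0 and to LLOQ × 24-h volume as bounds.

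A single LLOQ/2 value beside the bounds is optional. The sponsor should also say what counts as a complete collection, since the documents give no criterion.

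The urine volumes are already needed for Ae, so no new measurement is required. The cost is one replaced sentence and slightly more tabulation.

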9.3.2 Randomized Cohort

The primary and secondary efficacy endpoints that are continuous variables will be analyzed using paired t-test. All statistical tests will be two-sided and interpreted at a 5% significance level. A

p-value < 0.05 will be considered statistically significant. Unless stated otherwise, a two-sided 95% CI will be calculated and presented.

Categorical variables will be analyzed using McNemar's test for correlated proportions. In this intra-patient control study design, only discordant pairs of observations contribute to evidence of treatment effect. The appropriate test is an exact binomial calculation, using a 2-sided alpha of 0.05 or a 1-sided alpha of 0.025. In addition, frequency distributions showing findings by treatment side will be presented with counts, percentages and, where appropriate, exact 95% CI using the Clopper and Pearson method.

All available data at each time point will be presented. No imputations for missing data are planned, unless indicated otherwise. For the primary efficacy endpoint, if missing values exceed 10%, sensitivity analyses with imputations will be conducted. (see [Section 10.3.2.2](#)).

9.3.3 Relative Difference Calculation

Relative side-to-side difference at any timepoint will be calculated as:

$$[\text{Value}_{(\text{treatment side})} - \text{Value}_{(\text{control side})}] / \text{Value}_{(\text{control side})} \times 100$$

A negative relative difference reflects a decrease in a given parameter on the treatment side compared to control, while a positive relative difference reflects an increase in the parameter on the treatment side compared to control.

9.4 Determination of Sample Size

9.4.1 PK Cohort

The sample size for the PK cohort was selected without regard for statistical considerations. The sample of 5 treated subjects was deemed adequate to assess the quantifiable systemic exposure to MF when delivered from a UP Drug-Coated Device.

9.4.2 Randomized Cohort

The sample size was calculated based on the difference in the patency grade at Day 30 between the treatment and control sides with the following assumptions:

- Expected mean difference of 0.5 between the treatment and control sides in patency grade
- A SD of 1.1 for side-to-side difference in the patency grade of the FSO
- Target power of $\geq 90\%$
- Type I error rate of $\alpha = 0.05$, 2-sided

A mean difference in patency grade of 0.5 between the treatment and control sides favoring treatment sides was considered clinically meaningful. Based on standard formulas for a paired t-test, a sample size of 53 subjects provides at least 90% power to detect a difference of 0.5 in mean patency grade between treatment sides. Assuming up to 25% of subjects with non-evaluable data on one or both sides, additional 17 subjects will be enrolled for a total of 70 subjects in the randomized cohort.

9.5 Interim Analysis

There is no interim analysis planned for this study.

9.6 Coding Dictionaries

AE will be coded using the Medical Dictionary for Regulatory Activities (MedDRA, version 21.0 or later). Concomitant medications, will be coded using the March 2018 or later version of the World Health Organization (WHO) Drug Global dictionary.

10 STATISTICAL ANALYSES

10.1 Subject Disposition

The number and percentage of sinuses in which dilation with the UP Drug-Coated Device or UP Control Device was attempted, and those in which the dilation was successful will be summarized in each cohort. The primary reason for subject discontinuation will be summarized. Major protocol deviations will be incorporated into the subject disposition outputs. Screen failures will be reported in the data listings and not presented in the summary table. Data for subject disposition, including termination date and reason, will be listed.

10.2 Demographics and Baseline Clinical Characteristics

Demographic data (i.e., age, gender, race, ethnicity) and baseline clinical characteristics (i.e., number and extent of prior endoscopic sinus surgery (ESS), symptoms that have been present for ≥ 12 weeks prior to baseline, current status of asthma and allergic rhinitis diagnosed by physician, aspirin intolerance or allergy, any allergies, and history of smoking), history of repeated courses of corticosteroids and history of epistaxis will be presented for all subjects in each cohort. Lund-Mackay score, baseline patency and polypoid edema grades of the FSO will be summarized per treatment side.

10.3 Primary Endpoints

10.3.1 PK Cohort – Primary Endpoint

The primary endpoint is the number of successful sinus dilations of all attempted FSO using the UP Drug-Coated Device. The left and right sides of each subject will be considered independent, and each subject is expected to contribute up to 2 observations. The study will be considered successful if $\geq 80\%$ of attempted FSO are dilated successfully with no USADE related to the UP Drug-Coated Device. A successful FSO dilation is defined as insertion of the UP Drug-Coated Device into the targeted FSO followed by 2 consecutive complete inflations.

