8. Reposition the balloon distal to the first inflation site such that the proximal half of the balloon is in contact with sinus mucosa, adjacent to the first inflation site.
9. Repeat steps 5 and 6 to dilate the sinus ostium for a total of 2 inflations in each sinus ostium.
10. Retract the deflated balloon into the guide catheter before removing the dilation system out of the nostril (Note: Do not retract the tip of the UP Device beyond the blue tip marker on the guide catheter to prevent loss of the drug).

PK cohort: Subjects will undergo in-office bilateral sinus dilation with the UP Drug-Coated Device in the frontal sinuses with 2 inflations per sinus (total of 4 inflations per Device).

- Repeat steps 1 through 10 for each FSO with the same UP Drug-Coated Device. Note: Dilation of the maxillary and/or sphenoid sinus with the same UP Device may be performed, if clinically necessary. However, dilation of the maxillary and/or sphenoid sinuses must be performed only after dilation of the frontal sinuses.
- On the day of the baseline procedure, 4 additional blood draws (~ 11 ml at each timepoint) will be performed at 0.5 (\pm 5 min), 1 (\pm 5 min), 2 (\pm 10 min) and 4 (\pm 15 min)

hours following the end of the baseline procedure, defined as removal of UP Device from the nostril after successful dilation of both FSO in each subject.

Randomized cohort: Subjects will undergo an in-office sinus dilation with the UP Drug-Coated Device of the FSO randomized to treatment (2 inflations per device) while the contralateral FSO will serve as control and undergo sinus dilation with a UP Control Device (2 inflations per device).

- Steps 1 through 10 will be followed with each frontal side dilated with the assigned UP Device.

Postoperative care

PK cohort subjects will be required to collect urine samples for 24 hours following the baseline procedure.

After the baseline procedure, subjects in the PK cohort will be allowed and subjects in the randomized cohort will be required to use saline sprays/rinses/irrigations starting Day 2.

PK cohort subjects will not be allowed to use INCS sprays throughout the 30 days follow-up duration. Randomized cohort subjects will be allowed to use INCS sprays starting after the scheduled Day 14 study visit, if medically necessary.

Device disposal

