5 STUDY DESIGN

This is a prospective, multicenter clinical trial enrolling and treating a total of 75 subjects in two consecutive cohorts:

- PK Cohort (N=5): A non-randomized cohort to assess the systemic safety and performance of the UP Drug-Coated Device for in-office bilateral dilation of the FSO. Subsequently, the UP Drug-Coated Device may be used to dilate any sphenoid or maxillary sinuses, if clinically necessary. Subjects in the PK cohort will return for 6 follow-up visits at Day 1, 3, 7, 14, 21 and 30. Follow-up evaluations will include endoscopic examination, endoscopic grading, and patient-reported outcomes.
- Randomized Cohort (N=70): A randomized, intra-patient controlled, blinded cohort of 70 subjects to assess the safety and efficacy of the UP Drug-Coated Device used for in-office dilation of the FSO. The FSO randomized to the treatment (treatment side) will undergo dilation using the UP Drug-Coated Device while the contralateral FSO (control side) will be dilated with the UP Control Device without any coating and with identical dimensions of the balloon to that of the UP Drug-Coated Device. Subjects in the randomized cohort will return for 5 follow-up visits at Days 7, 14, 21, 30 and 60. Follow-up evaluation will include recorded endoscopic examination and endoscopic grading.

See [Appendix A](#) for Schedule of Assessments for both cohorts.

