10.4 Secondary Endpoints

10.4.1 PK Cohort

10.4.1.1 Endoscopic Outcomes Assessed by Clinical Investigators

Categorical measures will be analyzed as counts, proportions and frequencies and, where appropriate, 95% CI will be computed using exact methods.

The counts, proportion and frequency of the following outcomes will be presented per sinus side:

- Patency grade: sinuses with clinically significant stenosis/occlusion in the FSO (patency grade 0 or 1).

- Adhesion/scarring grade: sinuses with clinically significant amount of adhesion/scarring in the frontal recess/FSO (adhesion/scarring grade 2 or 3)
- Polypoid edema grade: sinuses with clinically significant amount of polypoid edema in the frontal recess/FSO (polypoid edema grade 2 or 3)
- Need for post-dilation intervention: proportion of sinuses that need post-dilation interventions in the frontal recess/FSO (e.g., steroid, surgical, repeat balloon dilation).

Post-dilation intervention is a composite endpoint that includes:

- Surgical interventions required to debride obstructive adhesions or scar tissue formation in the FSO (adhesion/scarring grade 2 or 3), and/or
- Oral steroid interventions warranted to resolve recurrent inflammation or polypoid edema in the frontal recess/FSO, and/or
- Repeat balloon dilation warranted to resolve clinically significant stenosis/occlusion of the FSO (patency grade 0 or 1)

Additional grouping for the above variables will also be analyzed.

Continuous measures will be analyzed using descriptive statistics such as means, SD, and, where appropriate, 95% CI, assuming a normal distribution for each timepoint. A change from baseline in patency, estimated FSO diameter, polypoid edema and inflammation score will be computed for each treated sinus.

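### PK cohort: a subject's two sinuses are declared independent, so secondary 95% intervals that pool both sides as 10 units would be too narrow

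*SAP*

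**What the plan says.** The PK cohort is described in SAP section 5 as "PK Cohort (N=5): A non-randomized cohort to assess the systemic safety and performance of the UP Drug-Coated Device". On its size, SAP 9.4.1 says: "The sample size for the PK cohort was selected without regard for statistical considerations".

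Under the PK primary endpoint, SAP 10.3.1 states: "The left and right sides of each subject will be considered independent, and each subject is expected to contribute up to 2 observations". Protocol 16.3 carries the same sentence. The success rule that follows requires that at least 80% "of attempted FSO are dilated successfully with no USADE related to the UP Drug-Coated Device". Protocol 16.3 describes the reporting: "The primary efficacy endpoint is the number of successful balloon dilations, which will be reported with descriptive statistics". No interval or test is attached to this endpoint.

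Protocol 11.2 instructs the operator in this cohort: "Repeat steps 1 through 10 for each FSO with the same UP Drug-Coated Device".

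Intervals appear in SAP 10.4.1.1, for secondary endoscopic outcomes graded by the clinical investigators. For categorical outcomes, tabulated by sinus side, "where appropriate, 95% CI will be computed using exact methods". Continuous outcomes may get normal-theory 95% intervals at each timepoint, again only where suitable. Changes from baseline in patency, estimated diameter, "polypoid edema and inflammation score will be computed for each treated sinus". Protocol 16.4 likewise foresees normal-theory intervals for the endoscopic measures, and its summaries include change from baseline in the PK cohort. Neither section mentions within-subject correlation or says whether left and right are combined.

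For the randomized cohort, SAP 9.3.2 prescribes the paired t-test and McNemar's test, both of which allow for correlation between a subject's two sides.

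**The concern.** Two frontal sinuses in one patient share the disease, the medication and, here, the device. Eligibility requires disease and obstruction on both sides (Protocol 10.2). One component of the post-dilation intervention composite, oral steroids (SAP 10.4.1.1), is a treatment of the whole patient. Positive correlation between sides is therefore to be expected, and the SAP allows for it in the randomized cohort.

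The only counting rule given for the PK cohort is two independent observations per subject. Carried into the secondary outcomes, it gives 10 units where there are 5 subjects, and the intervals then claim more precision than the data hold. This is the only cohort in which both frontal sinuses receive the drug-coated device, so readers may look to these intervals for the endoscopic course after bilateral treatment.

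**Working it through.** The plan states no interval width or precision target for this cohort, so there is no figure to reproduce. Its one numerical rule, at least 80% of attempted sinuses, means at least 8 of 10 when all 10 are attempted.

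**Inputs.** From the documents: 5 subjects (SAP 5), up to 2 sinuses each (SAP 10.3.1), 95% intervals, exact or normal-theory (SAP 10.4.1.1). Assumed: within-subject correlation ρ, which the documents do not give, taken over 0 to 1; and pooling of both sides, which they do not state.

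**Continuous outcomes, pooled t-interval.** The interval is mean ± t(0.975; 9) × s/√10. With 5 pairs:
- true variance of the mean = σ²(1 + ρ)/10
- expected value of s² = σ²(1 − ρ/9)
- ratio of the standard error used to the true one ≈ √[(1 − ρ/9)/(1 + ρ)]

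This ratio is √(0.967/1.3) = 0.86 at ρ = 0.3, √(0.944/1.5) = 0.79 at 0.5 and √(0.911/1.8) = 0.71 at 0.8. It is below 1 for any positive ρ. Simulation with normal data, 200,000 runs per row, compared the pooled interval (9 df) with one on the 5 subject means (4 df). Half-widths are in units of σ:

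| ρ | Pooled coverage | Subject-mean coverage | Pooled mean half-width | Subject-mean half-width |
|---|---|---|---|---|
| 0 | 95.0% | 95.1% | 0.70 | 0.82 |
| 0.3 | 91.5% | 95.1% | 0.68 | 0.94 |
| 0.5 | 88.6% | 94.9% | 0.67 | 1.01 |
| 0.8 | 83.5% | 95.0% | 0.65 | 1.11 |

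Part of the width difference is the loss of degrees of freedom: at ρ = 0 it is already 0.70 against 0.82.

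**Proportions, pooled exact interval.** For a true proportion p, each pair has both sides affected with probability p² + ρp(1 − p), neither side with (1 − p)² + ρp(1 − p), and exactly one side otherwise. Convolving five pairs gives the distribution of the count out of 10. Coverage of the Clopper-Pearson interval with n = 10 was enumerated for p from 0.02 to 0.98 in steps of 0.01:

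| ρ | Mean coverage | Minimum coverage |
|---|---|---|
| 0 | 98.3% | 96.2% |
| 0.3 | 96.5% | 92.7% |
| 0.5 | 95.1% | 89.7% |
| 0.8 | 92.8% | 84.3% |
| 1 | 91.1% | 80.9% |

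**If left and right are tabulated separately.** Each row has n = 5 and no subject counts twice, so correlation does not distort either interval. For example, 5/5 gives 0.478 to 1.

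**Primary rule.** It involves no interval. Correlation changes only the chance of reaching 8 of 10: from 0.383 (ρ = 0) to 0.421 (ρ = 0.5) at a true success rate of 0.7, and from 0.930 to 0.895 at 0.9.

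**The case against.** The strongest reply is that the independence sentence and the intervals sit in different places. The sentence belongs to the primary endpoint, where it serves mainly to define the denominator, and that endpoint is descriptive. SAP 10.4.1.1 does not repeat it, makes every interval conditional on suitability, and speaks of sinus sides, which could mean separate left and right tables. The table shells of SAP Appendix B might settle this, but only their titles are in the text available.

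Most of this stands, and it limits the point. A reader might infer three stronger things that the documents do not support:

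- *That the primary endpoint's precision is overstated.* No interval or test is planned for it.
- *That the secondary intervals are too narrow as a matter of fact.* This needs both pooling and positive correlation, and the first is not stated. For exact intervals, average coverage does not fall below 95% until the correlation exceeds about 0.5.
- *That the systemic exposure results are affected.* Plasma mometasone furoate, plasma cortisol and urinary cortisol are measured once per subject per sampling time or collection period.

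What the reply does not remove is the sentence itself. It is at odds with the use of one device for both sides and with the paired methods elsewhere in the SAP. It is also the only guidance an analyst has on counting sinuses in this cohort. Sides are not randomized here and both receive the same treatment, so combining them is the obvious course.

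**Conclusion.** Wrong as written, and minor. The independence statement in SAP 10.3.1 and Protocol 16.3 is not credible. If it is followed in the secondary endoscopic analyses, 10-sinus t-intervals cover less than 95% under any positive within-subject correlation: about 91.5%, 88.6% and 83.5% at 0.3, 0.5 and 0.8. Pooled exact intervals hold up better on average, but their minimum coverage is about 90% at 0.5 and 81% at full concordance.

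These figures rest on pooling of both sides, on correlations chosen for illustration and, for the t-intervals, on normal data. The consequence is confined to descriptive intervals in 5 subjects. The PK success rule, the four secondary endpoints intended for labelling (SAP 10.6) and all randomized-cohort results are untouched.

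**What to change.** - **SAP 10.3.1 and Protocol 16.3:** replace the independence statement with one that only defines the count, namely that each subject contributes up to two frontal sinuses. Change both documents, so that they stay in agreement.
- **SAP 10.4.1.1, continuous measures:** base the t-intervals on the mean of the two sides within each subject (n = 5).
- **SAP 10.4.1.1, proportions:** report per-sinus counts and percentages without a pooled interval, or give exact intervals for left and right separately (n = 5 each).
- **Optional:** the proportion of subjects with at least one affected side may be added, but only if labelled as a per-subject quantity. It is a different estimand from the per-sinus proportion.

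The cost is a few sentences in two documents and wider or fewer intervals. No data collection, sample size or test changes.
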